7.2 EVENT OF SPECIAL INTEREST – DIARRHEA

An increase in the frequency of BMs and loosening of the stool consistency from baseline are expected pharmacodynamic effects of plecanatide. These same attributes (increased stool frequency and looser stool consistency) are often used to define “diarrhea”; however, in light of significant inter-patient variability in bowel habit “phenotype” and wide differences in the perception of a “normal” bowel habit there is no standard definition of “diarrhea” for this patient population. An increase in frequency or consistency for one person is a welcome event while for another patient it might be bothersome “diarrhea”. In all cases, as mentioned in the NOTE

above, the frequency and consistency of each bowel movement is recorded in the electronic diary. However, this objective record often does not go far enough to characterize any change in bowel frequency or consistency as clinically important or impactful for the patient (whether beneficial or harmful).

One mechanism to introduce a level of consistency across patients, sites and the trial is to code an event as diarrhea only if it is characterized by a specific patient-reported and clinically relevant attribute such as “bothersomeness”. Therefore, for this trial, for any event associated with a significant increase from baseline in BM frequency and/or loosening of BM consistency - that would otherwise be coded as diarrhea - the site is instructed to record it as an AE only if the patient reports that it was bothersome (as defined by each patient).

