1 OVERALL DESIGN AND PLAN OF THE STUDY

This is an exploratory, randomized, double-blind, placebo-controlled, multicenter, parallel-group study of the efficacy and safety of 3 dose levels of plecanatide (0.5, 1.0, or 1.5 mg) in adolescent patients 12 to less than 18 years of age with CIC. Approximately 120 patients will be enrolled at approximately 40 study sites in the United States. Patient randomization will focus on the balanced enrollment of males and females across the 4 treatment groups.

The overall study plan is presented in Figure 1.

Figure 1 Study Design

After written informed consent/assent is obtained at Visit 1, patients will be screened for study eligibility. Qualifying patients will be instructed on the use of an electronic diary that will serve to record information on their daily bowel habits, rescue medication use and symptoms associated with CIC.

Patient will begin diary entries following Visit 1 and continue daily diary entries for the remainder of the study. The information recorded by the patient in the diary during the 2 weeks just prior to Visit 2 will confirm study eligibility, confirm diary compliance and establish baseline values for primary and secondary efficacy endpoints. The interval between Visit 1 (Screening) and Visit 2 (Randomization) should ideally be 28 days to ensure 2 weeks of 'diary practice' experience and 2 weeks for baseline diary recording. A minimum of 1 week of 'diary practice' is required prior to the 2-week baseline diary recording.

At Visit 2 (Day 1 of Treatment Period), patients who meet all study entry criteria will be randomly assigned to 1 of 4 treatment groups (3 active, 1 placebo) in a 1:1:1:1 ratio. The patients will take their first dose of study drug at the clinical site, and continue to take a single oral dose daily for 8 weeks. Supplies of the study drug will be replenished at the Week 4 Visit. At Weeks 4 and 8, patients will return to the clinic to undergo safety and efficacy assessments.

For 2 weeks after the last dose of study drug, patients will continue to complete their daily electronic diaries. Patients will return to the clinic for a final Follow-up visit at the end of Week 10.

The planned duration of participation in this study will be approximately 14 weeks (98 days) from signing of informed consent/assent through posttreatment.

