6.2 ADMINISTRATION

Study drug will be administered for 8 consecutive weeks according to the randomization scheme displayed in **Table 3**. Each patient will take one tablet orally (by mouth) daily preferably at the same time each day—**in the morning**—with approximately 240 mL (~8 oz.) of liquid, with or without food.

No dose adjustments will be allowed on this study.

Table 3 Treatment Arms

Table 3: Treatment Arms

Treatment Arm	Treatment	Number of Patients
1	0.5 mg plecanatide	30
2	1.0 mg plecanatide	30
3	1.5 mg plecanatide	30
4	Matching placebo	30

Overdose

Plecanatide has minimal systemic absorption, therefore standard treatment measures for the symptomatology being exhibited should be provided. Notable, plecanatide was generally well-tolerated after single doses up to 48.6 mg and multiple doses up to 9.0 mg for 12 weeks in prior studies.

Individual Patient Stopping Criteria

Adverse events due to study drug that affect individual patient safety may necessitate dose interruptions or early discontinuation as described in this section.

Plecanatide therapy in adults with CIC has caused diarrhea in 5% of patients with severe diarrhea occurring in 0.6% of patients. Severe diarrhea may cause dehydration. Pediatric patients may be at increased risk for diarrhea and dehydration with plecanatide therapy.

In general, study drug dosing should not be modified for mild diarrhea (Grade 1: increase of <4 stools per day over baseline) or mild dehydration (Grade 1: dry mucous membranes, diminished skin turgor) (Guidance for Industry, FDA, 2007). If study drug is not well tolerated by an individual patient, treatment will be permanently discontinued for that patient.

The following guidelines should be used in the case of moderate or severe diarrhea or dehydration:

Table 4 Individual Patient Stopping Criteria

Worst Observed Toxicity Grade (Guidance for Industry, FDA, 2007)	Dose Modification for Study Drug
Diarrhea	
Grade 2: Increase of 4-6 stools per day over baseline	No intervention required
Grade 3: Increase of ≥ 7 stools per day over baseline, incontinence, hospitalization indicated	Interrupt study drug for <7 days until resolved to less than Grade 2 severity. If diarrhea was study drug-related, permanently discontinue study drug. If diarrhea was not study drug-related, eg, viral gastroenteritis, then consider resuming treatment after consultation with Sponsor's Medical Monitor

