Grade 4: Life-threatening consequences, urgent intervention indicated	Permanently discontinue study drug
Dehydration	
Grade 2: IV fluids indicated <24 hour	Interrupt study drug for <7 days until resolved to less than Grade 2 severity. If dehydration was study drug-related, permanently discontinue study drug. If dehydration was not study drug-related, consider resuming treatment after consultation with Sponsor's Medical Monitor
Grade 3: IV fluids or hospitalization indicated	Permanently discontinue study drug
Grade 4: Life-threatening consequences, urgent intervention indicated	Permanently discontinue study drug

Study Stopping Criteria

Dosing of all patients in the study will be interrupted for at least one week if ≥ 2 patients receiving study drug develop drug-related Grade 3 diarrhea and/or dehydration or if one patient

develops drug-related Grade 4 diarrhea and/or dehydration. This will allow the Sponsor to assess whether the trial should be stopped or modified.

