7.3.3 Causality

The investigator will assess the causality/relationship between the study drug, or study procedure, and the AE and record that assessment in the eCRF.

The causal relationship of the AE to study drug will be described in terms of:

Reasonable Possibility: There is evidence to suggest a causal relationship between the drug and the AE (e.g., the AE is uncommon and known to be strongly associated with drug exposure or is uncommon in the study population but not commonly associated with drug exposure)

No Reasonable Possibility: There is no evidence to suggest a causal relationship between the drug and the AE

The study conduct relatedness for AEs and SAEs will also be assessed and documented. The most likely cause of an AE or SAE (e.g., disease under treatment, concomitant disease,

concomitant medication, other) will be indicated in the eCRF system with details of the concomitant disease or medication or other cause.

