7.4 RECORDING ADVERSE EVENTS

Adverse event assessment and reporting will extend from signing of ICF until completion of the final visit (End of the Posttreatment Period). Adverse events occurring from the time of ICF signing up to the intake of the first dose of study medication will be classified as pre-existing conditions for this study and therefore will be recorded in the Medical History page of the eCRF. If, however, an event is considered a Serious Adverse Event (as defined below), and occurs after the signing of informed consent but before randomization (i.e., during screening), this will be collected and reported as non-treatment-emergent Serious Adverse Events, and will be recorded in the Adverse Event page of the eCRF. Events that occur from time of first dose of study drug until completion of the final study visit will be considered Treatment-Emergent Adverse Events, and recorded on the AE page of the eCRF. Adverse events occurring after the end of the study should be reported to the Sponsor by the Investigator only if the event meets at least one seriousness criterion and the Investigator considers the causal relationship to the study drug as 'reasonably possible'.

All AE reports should contain a brief description of the event, date of onset, date of resolution, intensity, treatment required, relationship to study drug, action taken with the study drug, outcome, and whether the event is classified as serious.

All AEs experienced by patients who are randomized to treatment, regardless of the relationship to study drug, will be recorded in the eCRF. For patients who are screen failures, only SAEs (if any) will be reported on the AE page of the eCRF.

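### Section 7.2 keeps non-bothersome diarrhea off the AE page even at Table 4 Grade 3, so a non-serious case has no AE entry or recorded causality to count toward the two-patient study pause

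*Combined protocol and SAP*

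**What the plan says.** **Recording rule (Section 7.2).** More frequent and looser stools are expected effects of the drug, so the protocol uses the patient's own sense of bother to decide what counts as diarrhea. For an event that would otherwise be coded as diarrhea, the site is to "record it as an AE only if the patient reports that it was bothersome (as defined by each patient"). No grade, stool count or other sign overrides this.

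**Grades (Section 6.2, Table 4).** Grade 3 diarrhea is a rise of 7 or more "stools per day over baseline, incontinence, hospitalization indicated". Bother is not part of the definition. Grade 3 is the first diarrhea grade that requires action: interrupt the drug, and stop it permanently if the diarrhea was drug-related. The only contact Table 4 names for Grade 3 diarrhea is on the unrelated branch: "If diarrhea was not study drug-related, eg, viral gastroenteritis, then consider resuming treatment after consultation with" the Medical Monitor.

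**Study pause (Section 6.2, Study Stopping Criteria).** Dosing stops for everyone for at least a week if two or more "patients receiving study drug develop drug-related Grade 3 diarrhea and/or dehydration", or if one patient has a drug-related Grade 4 event.

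**Where causality and severity are recorded.** Section 7.3.3: "The investigator will assess the causality/relationship between the study drug, or study procedure, and the AE and record that assessment in the eCRF". Section 7.4: "All AE reports should contain a brief description of the event, date of onset, date of resolution, intensity, treatment required, relationship to study drug", followed by action taken, outcome and seriousness. Section 7.3.2 defines intensity as mild, moderate or severe.

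**The concern.** The recording rule and the pause use different tests for the same event. Section 7.2 asks whether the adolescent was bothered. The pause asks whether the event was Grade 3 and drug-related, and Grade 3 is defined without bother. An event can therefore meet the pause definition and still, on the plain words of Section 7.2, be kept off the AE page.

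This matters because the pause is a count across the whole study. Someone has to see both cases, know that each was Grade 3, and know that each was judged drug-related. With a threshold of two, one case without a shared record can leave the count at one. Section 6.2 itself says that pediatric patients may be at higher risk of diarrhea and dehydration. No interim analysis is planned, and this is the only study-level stopping rule in the protocol with a numeric trigger.

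**Working it through.** The protocol gives no figure on this point to reproduce. The check follows one episode through the text, then gives a sense of scale.

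**Tracing a non-serious Grade 3 episode that the patient does not call bothersome**

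| Step | Section | Result |
|---|---|---|
| Does it meet Table 4 Grade 3? | 6.2 | Yes, by stool count or incontinence |
| Must a site that knows of it act? | 6.2 | Yes: interrupt, judge relatedness, stop if related |
| Is it entered as an AE? | 7.2 | No |
| Is severity or causality recorded? | 7.3 to 7.4 | No; these attach to AEs |
| Does 24-hour SAE reporting catch it? | 7.3.1, 7.5 | No; non-serious by construction |
| Is another trace left? | 5.2.6 | Normally a withdrawal reason if the drug is stopped; no grade or causality field is specified |
| Is anyone assigned to compare on-treatment diary counts with Table 4? | 5.2.3, 5.2.4, 8.6 | Not in the protocol; the diary review it states is for entry compliance |

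**The grade, for all events.** The Section 7.4 list has intensity but no Table 4 grade. Section 6.2 partly links the two scales ("study drug dosing should not be modified for mild diarrhea (Grade 1: increase of <4 stools per day over baseline"), but Section 7.3.2 gives no stool counts. So a bothersome diarrhea AE or a dehydration AE is also recorded without the grade the pause uses. Section 7.2 does not cause this.

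**What Grade 3 by count means here.** Entry allows at most 2 SBMs in each baseline week: 2/7 = 0.29 per day. Grade 3 by count is then about 7 + 0.29 = 7.29, or roughly 7 to 8 stools in a day (slightly more if stools after rescue laxative count in baseline).

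**Size of the trigger.** Three plecanatide arms of 30 give 90 patients; 2/90 = 2.2%.

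**Scale (illustration).** Let p be the rate of drug-related Grade 3 diarrhea on plecanatide and f the share of cases not recorded because they were not bothersome. The number counted is taken as binomial with n = 90 and probability p(1 − f), and

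P(two or more) = 1 − (1 − q)^90 − 90q(1 − q)^89, with q = p(1 − f).

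The documents give neither p nor f. For p, the adult severe-diarrhea figures of 0.4% and 0.7% (Section 2.1.4) and 0.6% (Section 6.2) stand in, read as per-patient rates. The 2% row is a further assumption, to show a higher rate.

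| p | Expected cases, 90p | f = 0 | f = 5% | f = 10% | f = 25% | f = 50% |
|---|---|---|---|---|---|---|
| 0.4% | 0.36 | 5.1% | 4.6% | 4.2% | 3.0% | 1.4% |
| 0.6% | 0.54 | 10.2% | 9.4% | 8.6% | 6.3% | 3.0% |
| 0.7% | 0.63 | 13.1% | 12.1% | 11.1% | 8.2% | 4.0% |
| 2% | 1.80 | 54% | 51% | 48% | 39% | 23% |

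At the adult rates, f of 5% to 10% lowers the chance of counting two by 0.4 points (5.1 to 4.6 before rounding) up to 2.0 points (13.1 to 11.1). The loss is large only if both p and f are well above what seems likely.

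**The case against.** The best case for the plan has four parts.

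*Table 4 does not depend on an AE entry.* It works on the worst grade observed and forces a relatedness decision. A reader might infer from Section 7.2 that such an episode would be neither graded nor judged for causality. The text does not support that: an investigator who knows of it must do both to follow Table 4, and stopping the drug normally leads to an early-withdrawal visit and a recorded reason. Section 6.2 also presents its rules as concerning adverse events, so an event that stops the drug could be read as an AE whatever Section 7.2 says. This stands in part. What is missing is a specified record of grade and causality that can be counted across sites.

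*The affected group is small.* A patient who entered with at most two SBMs a week must pass seven or more extra stools in a day, or be incontinent, and say it was not bothersome. The event must also be non-serious and, to escape the pause count altogether, without a drug-related Grade 3 dehydration AE, since Section 7.2 does not restrict dehydration. Open questioning at visits, laboratory tests, examinations and the two-week incontinence question are further backstops, though none checks stool counts. This stands and limits the severity.

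*Spread over sites is not the defect.* The plan says "Approximately 120 patients will be enrolled at approximately 40 study sites in the United States", so with equal enrollment two random patients share a site only 2/119 = 1.7% of the time. A reader might take that as the share of cases lost. It is not: it applies equally to properly recorded bothersome cases, and shows only why a shared record is needed.

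*Silence on diary review proves little.* The Study Procedure Manual, the final diary specifications and the separate SAP were not available. Stool counts are captured daily and may be reviewed under one of those. This stands; the point is limited to what the protocol states.

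**Conclusion.** The point holds in a narrow form. A stated rule in Section 7.2 removes the AE entry, and with it the recorded causality assessment, from a class of events that Section 6.2 counts toward pausing the study. Separately, AE reports of any kind lack the Table 4 grade. It would be wrong to conclude that the bothersome rule disables the pause or that many Grade 3 events will be lost. The documents give no rate for non-bothersome Grade 3 diarrhea, and it is probably low. At the adult severe-diarrhea rates, with 5% to 10% of cases not bothersome, the pause would be about 0.4 to 2 percentage points less likely to trigger. That range assumes that adult severe diarrhea stands for drug-related Grade 3 in adolescents, and that unrecorded cases are not counted by any other route. The bothersome rule is reasoned and suits lower-grade stool changes. The change is worth making because a study-level safeguard in adolescents should not turn on each patient's own definition of bother, and because it costs little.

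**What to change.** - In Sections 7.2 and 7.4, require every known diarrhea event of Table 4 Grade 3 or higher to be entered on the AE page with its grade and a causality assessment, whether or not the patient found it bothersome.
- Add the Table 4 grade to all diarrhea and dehydration AEs, and tabulate it in Section 8.10.
- Keep the bothersome rule for lower grades, and leave the clinical action at each grade as it is.
- Optional, if the system supports it: an eDiary flag to the site and Medical Monitor at 7 or more BMs per day over baseline.

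The cost is a short amendment, one eCRF field and a few more listed diarrhea AEs. Dosing, sample size and efficacy analyses do not change. The AE-page change helps only for episodes the site learns of. Finding the others depends on the eDiary flag, whose cost cannot be judged from the documents, or on procedures in manuals not available here.

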7.3 ASSESSMENT OF ADVERSE EVENTS

Each AE will be assessed by the Investigator with regard to the following categories.

7.3.1 Seriousness

An SAE is defined as any untoward medical occurrence that at any dose is one of the following:

- Results in death
- Is life threatening (an adverse event or suspected adverse reaction is considered “life threatening” if, in the view of either the investigator or sponsor, its occurrence places the patient or subject at immediate risk of death. It does not include an adverse event or suspected adverse reaction that, had it occurred in a more severe form, might have caused death)
- Requires inpatient hospitalization or prolongation of existing hospitalization
- Results in a persistent or significant incapacity or substantial disruption of the ability to conduct normal life functions
- Is a congenital anomaly or birth defect
- Is a medically important event (examples of such medical events include allergic bronchospasm requiring intensive treatment in an emergency room or at home, blood dyscrasias or convulsions that do not result in inpatient hospitalization, or the development of drug dependency or drug abuse)

The FDA has recently defined additional “**Medically Important Events**” that should also be reported as SAEs (Guidance for Industry, FDA, July 2009). These include cases where:

- Aminotransferases (ALT or AST) are > 3 times the upper limit of normal (ULN) with an associated elevation of total bilirubin > 2 times ULN without evidence of hemolysis or with alkaline phosphatase < 2 times ULN or not available, or
- ALT or AST activity that is > 5 times ULN

All subjects with the above abnormalities should return as soon as possible or within 48 hours to the site for further evaluation of the abnormalities, including repeat ALT and AST measurements; total and direct bilirubin; alkaline phosphatase; and related laboratory assessments of albumin, PT and PTT, creatinine kinase, and GGTP or 5' nucleotidase. Hepatitis A, B, and C, hemolysis, and biliary obstruction should be ruled out. A detailed medical and drug

use history should be taken to exclude all potential causes. All such laboratory tests should be performed locally if they are not listed in **Section 4.3.2; Table 1**.

Medical and scientific judgment should be exercised in deciding whether a case is serious and whether expedited reporting is appropriate as in the example above for “**Medically Important Event**.” The medical monitor should be consulted.

7.3.2 Intensity (Severity)

Investigators should assess the severity of AEs according to the following general categorical descriptors:

Mild: Asymptomatic or mild symptoms; clinical or diagnostic observations only; intervention not indicated

Moderate: Minimal, local, or noninvasive intervention indicated; limiting age appropriate instrumental activities of daily living (ADL) (instrumental ADL includes preparing meals, shopping for groceries or clothes, using the telephone, managing money, etc.)

Severe: Medically significant but not immediately life-threatening; hospitalization or prolongation of hospitalization indicated; disabling; limiting self-care ADL (self-care ADL includes bathing, dressing and undressing, feeding self, using the toilet, taking medications, and not bedridden)

It is important to distinguish between serious and severe AEs. Severity is a measure of intensity, whereas seriousness is a regulatory definition as per **Section 7.3.1**. An AE of severe intensity may not necessarily be considered serious (by definition) or a mild AE (mild stroke) may be considered an SAE.

7.3.3 Causality

The investigator will assess the causality/relationship between the study drug, or study procedure, and the AE and record that assessment in the eCRF.

The causal relationship of the AE to study drug will be described in terms of:

Reasonable Possibility: There is evidence to suggest a causal relationship between the drug and the AE (e.g., the AE is uncommon and known to be strongly associated with drug exposure or is uncommon in the study population but not commonly associated with drug exposure)

No Reasonable Possibility: There is no evidence to suggest a causal relationship between the drug and the AE

The study conduct relatedness for AEs and SAEs will also be assessed and documented. The most likely cause of an AE or SAE (e.g., disease under treatment, concomitant disease,

concomitant medication, other) will be indicated in the eCRF system with details of the concomitant disease or medication or other cause.

